2 STUDY OBJECTIVES AND ENDPOINTS

OBJECTIVES	ENDPOINTS
Primary	
To compare the efficacy and tolerability of a 24 mg total daily dose of CTP- 543 utilizing two different	Primary efficacy endpoint in each dose regimen: • Relative change in Severity of Alopecia Tool (SALT) score for each dose regimen from Baseline at Week 24.
dosing regimens in adult	Tolerability endpoints in each dose regimen:
patients with chronic, moderate to severe alopecia areata.	• Adverse events (AEs), vital signs, concomitant medications, clinical laboratories, and electrocardiogram (ECG) results, as well as physical examinations
Secondary/Exploratory	
To assess the proportion of	Secondary efficacy endpoints in each dose regimen:
patients achieving defined threshold reductions in SALT score, and for	• Proportion of patients achieving at least a 90%, 75%, and 50% reduction in SALT score from Baseline at Weeks:
patients to assess their	o 4, 8, 12, 16, 20, and 24 in the Treatment Period
eyebrows, hair coverage and hair coverage quality.	 Absolute change in SALT scores from Baseline at Weeks: 4, 8, 12, 16, 20, and 24 in the Treatment Period

	STATISTICAL ANALYSIS PLAN, Final v1.0	
Protocol Number CP543.2003	Sponsor: Concert Pharmaceuticals, Inc.	

OBJECTIVES	ENDPOINTS	
	Relative change in SALT scores from Baseline at Weeks:	
	o 4, 8, 12, 16, and 20 in the Treatment Period	
	 Change in satisfaction of hair coverage as reported by the patient from Baseline to Weeks 8, 12, and 24 	
	Exploratory efficacy endpoints in each dose regimen:	
	• Change in patient's eyebrows as measured by the patient's Visual Analog Scale (VAS) from Baseline to Weeks 12 and 24	
	 Change in satisfaction of hair coverage quality as reported by patient from Baseline to Weeks 8, 12, and 24 	

3 STUDY DESIGN

3.1 Overall Design

This is a randomized, parallel-group, multicenter study to evaluate the efficacy and tolerability of two dosing regimens of CTP-543 (12 mg twice daily [BID] vs 24 mg once daily [QD]) in adult patients with chronic, moderate to severe alopecia areata. Patients will be between 18 and 65 years of age and experiencing an episode of alopecia areata lasting at least 6 months and not exceeding 10 years, with at least 50% hair loss as measured by the Severity of Alopecia Tool (SALT) at Screening and Baseline, and are not concurrently being treated for alopecia areata with other treatments that might affect hair regrowth or immune response. Up to approximately 75% of alopecia areata patients with alopecia totalis or universalis, and no more than 10% of patients with alopecia ophiasis will be enrolled.

A full list of the inclusion and exclusion criteria can be found in Sections 7.1 and 7.2 in the CP543.2003 Protocol.

Patients may be screened up to 28 days prior to initiation of study drug. The Treatment Period is a 24-week dosing period where patients will be randomized to receive either 12 mg BID or 24 mg OD of CTP-543.

[figure not shown]
[figure not shown]

Figure 1: Study Design

Patients will provide informed consent prior to completing any screening procedures. Patients meeting screening criteria will continue to the Day 1 Randomization Visit for review of eligibility and Baseline assessments. Patients meeting all eligibility criteria will be randomized to receive either 12 mg BID CTP-543 or 24 mg QD CTP-543 in a 1:1 ratio. Approximately 60 patients are planned to be randomized in the study (i.e., approximately 30 patients per dosing regimen).

Patients will take the first dose of study drug in the clinic on Day 1 and will be instructed to take study drug every 12 hours. To minimize the bias in the evaluation of study endpoints, patients, investigators, and site personnel will be unaware of the active drug dosing regimen by administering 2 x 12 mg tablets and 2 x placebo tablets 12 hours apart from each other for the 24 mg QD study drug. Patients should dose study drug in the clinic on all Study Visit Days after clinical laboratory blood draws are completed.

Patient safety will be monitored throughout the trial. Significant cytopenias or other hematologic abnormalities will be managed by severity through dose interruption, or discontinuation, and signs and symptoms of infection will be closely monitored and treated promptly. Patients who experience intolerable symptoms during treatment may discontinue the study at the discretion of the Investigator. Patients may withdraw consent at any time. A patient who prematurely discontinues study drug should have all Week 24 assessments performed as an Early Termination (ET) visit and return for the Safety Follow-up Visit. The Safety Follow-Up Visit may be waived by the Sponsor in instances where patients have discontinued dosing prior to the ET visit on a case-by-case basis.

	STATISTICAL ANALYSIS PLAN, Final v1.0
Protocol Number CP543.2003	Sponsor: Concert Pharmaceuticals, Inc.

Upon completion of the 24-week Treatment Period, patients will be eligible to either complete treatment and exit the study following the safety follow-up visit, or roll-over into an open-label extension study.

Appendix 1 provides a description of the procedures planned at each visit.

3.2 Treatment Regimens

CTP-543 will be dosed orally as tablets. Doses and frequency will be allocated as follows:

- 12 mg BID CTP-543 (1 x 12 mg and 1 x placebo tablet every 12 hours)
- 24 mg QD CTP-543 (2 x 12 mg in the mornings and 2 x placebo tablets in the evenings)

3.3 Randomization, Replacement, and Unblinding Procedures

Patients meeting all inclusion criteria and none of the exclusion criteria will be randomized to 12 mg BID CTP-543 or 24 mg QD CTP-543 in a 1:1 ratio. Randomization will be stratified by classification of alopecia areata subtype into one of the following three categories: 1) alopecia areata, 2) alopecia totalis or alopecia universalis, or 3) alopecia ophiasis.

Patients who withdraw or are withdrawn from the study will not be replaced.

To maintain the blind for investigators, subjects, and site personnel, subjects will take their randomized treatment in the am and pm no matter which regimen they are randomized to. The Clinical Research Organization (CRO) study team will also remain blinded to the dosing regimen until database lock.

The study will be unblinded after approval of the SAP, clinical trial data are entered into the database, any discrepancies in the data are resolved, determination of the inclusion/exclusion of each subject from each analysis population and lock of the database.

3.4 Changes to the Analysis from the Protocol

The Efficacy analysis population described in the synopsis of the protocol is referred to as the modified Intent-to-Treat (mITT) analysis population in Section 11.3 of the protocol. To avoid confusion, this analysis population will be called the mITT analysis population in this SAP as well as in the statistical outputs.

As per Section 11.4.3 of the protocol, the total number of days on study drug will exclude dose interruptions. However, dose interruptions will not be excluded from the duration of exposure to the study drug as specified in Section 11, in order to be in line with industry's standards.

	STATISTICAL ANALYSIS PLAN, Final v1.0
Protocol Number CP543.2003	Sponsor: Concert Pharmaceuticals, Inc.

As per Section 11.4.4 of the protocol, treatment-emergent AEs (TEAEs) are defined as any AE that occurs after administration of the first dose of study drug until Week 24 or Early Termination Visit. However, TEAEs will be defined as any AEs with onset date/time on or after the first dose of study drug (refer to Section 13.1), in order to be in line with the industry's standards.

As per Section 11.4.4 of the protocol, the number and percentage of patients with abnormal, clinically significant laboratory values (per Investigator judgment) will be summarized by dosing regimen for each clinical laboratory variable. This summary has been replaced by shift tables from Baseline to the worst post-Baseline result describing shifts to abnormality as assessed by the central laboratory (low, normal, high) (refer to Section 13.2). Abnormal, clinically significant laboratory values (per Investigator judgement) will be identified in by-patient data listing.

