# Patients who require a dose interruption lasting more than 21 consecutive days will be discontinued from the study.

Patients who are discontinued from the study should undergo an Early Termination Visit and subsequent Safety Follow-up Visit as appropriate per Section 7.3.1 Patient Withdrawal Procedures, and associated adverse events followed as described in See Section 10 Adverse Events.

Hematology and serum chemistry parameters will be assessed every 2 weeks for the first 8 weeks of the Treatment, and every 4 weeks thereafter for the remainder of the study. Prior to dose interruption, hematology parameters should be confirmed with repeat testing at an interval deemed appropriate by the Investigator (e.g., at the next protocol-defined visit or an Unscheduled Visit), except in severe cases where immediate interruption of dosing is necessary for the safety of the patient. Blood draws confirming dose interruption criteria should occur prior to the first daily dose on the day of draw.

Dose interruption requirements for hematologic abnormalities are provided below. However, less significant changes may warrant clinical intervention and the Investigator should use his/her best clinical judgment when considering a dose interruption whether for singular or aggregate hematology results above the limits provided in Table 3, or for other clinical signs, symptoms, or considerations that suggest dose interruption is in the best interest of the patient.

Table 3: Selected Hematologic Thresholds for Dose Interruption

Neutrophil Count	Dose Adjustment		
Less than 1 x 10  /L	Interrupt dose until recovered to greater than $1.5 \times 10^9$ /L and resume dosing at previous dose		
Female Hemoglobin Level	Dose Adjustment		
Less than 10 g/dL	Interrupt dose until recovered to greater than 11.5 g/dL and resume dosing at previous dose		
Male Hemoglobin Level	Dose Adjustment		
Less than 11.5 g/dL	Interrupt dose until recovered to greater than 13 g/dL and resume dosing at previous dose		
Platelet Count	Dose Adjustment		
Less than 75 x 10  /L	Interrupt dose until recovered to greater than 75 x 10  /L and resume dosing at previous dose		
Greater than 750 x 10  /L	Interrupt dose until recovered to less than 600 x 10  /L and resume dosing at previous dose		

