#### 11.4.3. Study Drug Exposure

For each patient, the number of days of exposure to CTP-543 will be summed across the Treatment Period. The total number of days on study drug will exclude dose interruptions. The total number of days of exposure to CTP-543 will be summarized with the mean, standard deviation, median, minimum, and maximum number of days on the dose. Drug compliance will also be summarized.

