11 STUDY TREATMENT EXPOSURE AND TREATMENT COMPLIANCE

A summary of exposure to study drug (days) will be presented by dosing regimen based on the Safety analysis population. Exposure to study drug, in days, will be computed as follows:

[(Date of last dose of study drug – Date of first dose of study drug) + 1]

Compliance with study drug (%) will be calculated as follow:

Number of tablets taken x 100%
Total number of tablets planned to be taken

where the number of tablets taken is defined as the total number of tablets dispensed minus the total number of tablets returned, and total number of tablets planned to be taken is defined as the exposure to study drug multiplied by the number of planned tablets per dose (i.e., 2).

Descriptive statistics for the compliance to study drug will be presented by dosing regimen based on the Safety population. Frequency distribution will also be presented for the following categories: < 80%, 80% - 120%, and > 120%.

Exposure and compliance will be displayed in a listing of study treatment administration.

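### The SAP counts dose-interruption days as exposure and, in the compliance formula, as days with planned tablets, and leaves no summary table of time off drug (minor)

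*SAP*

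**What the plan says.** On days on drug, Protocol 11.4.3 is explicit: "The total number of days on study drug will exclude dose interruptions". It adds that drug compliance will be summarized but defines no denominator for it.

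SAP 3.4 acknowledges that rule and replaces it: "However, dose interruptions will not be excluded from the duration of exposure to the study drug as specified in Section 11". The only reason given is "in order to be in line with industry's standards".

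SAP 11 computes exposure as "Date of last dose of study drug – Date of first dose of study drug) + 1". For compliance, the numerator is "the total number of tablets dispensed minus the total number of tablets returned" and the planned tablets are the "exposure to study drug multiplied by the number of planned tablets per dose (i.e., 2"). The results are shown as a mean and in three categories: below 80%, 80% to 120%, and above 120%.

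Protocol 8.2 provides for interruption when hematologic thresholds are crossed and limits its length: "Patients who require a dose interruption lasting more than 21 consecutive days will be discontinued from the study". A later interruption in the same patient is possible after discussion with the Medical Monitor.

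**The concern.** Interruption followed by resumed dosing is one of the protocol's responses to hematologic toxicity, and tolerability shares the primary objective with efficacy. How long patients were off drug is therefore something a reader of this trial will want to see by regimen. Days on drug under Protocol 11.4.3 was the one planned summary that reflected it. Under the SAP, a patient who stopped for three weeks and restarted has the same exposure as one who never stopped.

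The change also carries into compliance, which SAP 3.4 does not mention. Because the calendar span feeds the denominator, days on which the patient was told not to dose add planned tablets. They act like missed tablets in a figure that is meant to describe adherence.

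What remains in SAP 13.1 is a count of patients with a TEAE leading to interruption, in the overall AE table. The protocol's breakdown of those events by system organ class and preferred term (Protocol 11.4.4) and its listing of them (Protocol synopsis, tolerability analyses) do not appear among the SAP 13.1 outputs. SAP 3.4 declares neither omission.

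**Working it through.** **Inputs**
- Treatment duration: 24 weeks = 168 days (Protocol synopsis).
- Tablets: 2 per dose, two doses a day, in both arms (SAP 3.2), so 4 per day.
- Longest single interruption after which a patient may continue: 21 days (Protocol 8.2).
- Patients per arm: about 30 (SAP 3.1).
- Assumptions: the patient takes every tablet outside the interruption and resumes dosing afterwards. An interruption that ends in discontinuation adds nothing, because exposure stops at the last dose taken.

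**1. The SAP formula as written**
- Planned tablets by SAP 11: 168 × 2 = 336.
- Planned tablets by the dosing text: 168 × 4 = 672.
- A fully adherent patient scores 672/336 = 200%. The factor of 2 tablets per dose is applied to days instead of doses. This is a separate error, but it sits in the same denominator.
- With one 21-day interruption, tablets taken are 147 × 4 = 588, and 588/336 = 175%.

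**2. One patient, at 4 tablets per day**
- Exposure by the SAP: 168 days. Days on drug by Protocol 11.4.3: 168 − 21 = 147. The ratio 168/147 = 1.143, so the SAP figure is 14.3% higher.
- Compliance with interruption days kept: 588/672 = 87.5%. With them excluded: 588/588 = 100%.
- Excluding interruptions but keeping the factor 2 gives 588/(147 × 2) = 200%, so neither correction is enough alone.

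**3. When the category changes, at 4 tablets per day**
- With d days off in 168, compliance is (168 − d)/168. It is 135/168 = 80.4% at d = 33 and 134/168 = 79.8% at d = 34. Falling below 80% needs at least 34 days off, hence more than one interruption. Two of 21 days give 126/168 = 75%.
- With 21 days off and a last dose on Day T, compliance is (T − 21)/T. It is 84/105 = 80.0% at T = 105 and 83/104 = 79.8% at T = 104. A patient with a last dose before Day 105 falls below 80%; at T = 84 the figure is 63/84 = 75%.

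**4. Arm level**

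Assume that k of 30 patients each have 21 days off and that all 30 have a 168-day span. Mean exposure by the SAP exceeds mean days on drug by 21k/30 days. Mean compliance at 4 tablets per day falls by 12.5k/30 points.

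| k of 30 | Mean exposure higher by (days) | As % of 168 | Mean compliance lower by (points) |
|---|---|---|---|
| 1 | 0.7 | 0.4 | 0.4 |
| 3 | 2.1 | 1.25 | 1.25 |
| 6 | 4.2 | 2.5 | 2.5 |
| 10 | 7.0 | 4.2 | 4.2 |

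**5. Other results that could be affected**

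SAP 6.2 bases percentages on patients in the analysis population, and SAP 13.1 and 13.2 report patients with events. No AE or laboratory percentage has exposure days as its denominator, so the effect on them is zero.

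**The case against.** The sponsor has a fair case. The change is declared, was written before database lock and unblinding, and applies alike to both arms. Last dose minus first dose plus 1 is a legitimate measure of treatment duration. Exposure and compliance are not among the tolerability endpoints in SAP 2. Patients with a TEAE leading to interruption are still counted by regimen, laboratory values that led to interruption are flagged in listings (SAP 13.2), and treatment administration is listed (SAP 11). On compliance there is no departure from the protocol, which defines no denominator. The only experience reported, from the ongoing study at 12 mg BID, shows no interruptions for hematologic abnormalities (Protocol 4.2.1).

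Most of this stands, and it limits the point. It does not remove it:
- A listing is not a summary, and a count of patients says nothing about length of time off drug.
- The same formula in both arms gives different results if interruptions differ by arm.
- The 12 mg BID experience was early: the first enrolled subject had reached 16 weeks. For 24 mg QD, the documents describe only 7 days in healthy volunteers (Protocol 4.4.1), so its interruption rate in patients is unknown.

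A reader might infer that the change distorts the tolerability comparison or hides a toxicity difference between regimens. The documents do not support that: AE and laboratory percentages are untouched, and a difference in the number of patients interrupting because of an AE would still show. A reader might also infer that interrupted patients will be reported as poor adherers. Under the formula as written they score 175% and fall above 120%. Lower compliance in the expected range appears only once the tablets-per-day error is corrected, and even then one 21-day interruption over 168 days stays within 80% to 120%.

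**Conclusion.** The point holds as a minor one. The SAP replaces the protocol's days on drug with a calendar span, carries that span into the compliance denominator without saying so, and leaves no summary table of time off drug. For a single patient the effect can be material: 168 against 147 days, and 87.5% against 100%, for one 21-day interruption over full treatment. At arm level it is likely to be small, 0.7 to 7.0 days and 0.4 to 4.2 points across the assumed range of 1 to 10 patients in 30. A between-arm difference arises only if interruptions differ by arm.

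These figures rest on full adherence outside the interruption, resumed dosing, and 4 planned tablets a day. The documents give no interruption frequency for this trial, so the arm-level range is illustrative.

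**What to change.** In SAP 11:
- Keep calendar duration as now defined.
- Add, by regimen, total days interrupted per patient and days on drug excluding interruptions, as in Protocol 11.4.3.
- Define planned tablets as 4 × days on drug, where the days removed are investigator-directed interruptions only. Doses that the patient skips stay in the denominator. This also corrects the factor of 2; the two corrections must be made together.

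Amend the exposure paragraph of SAP 3.4 to say that both measures are reported and how interruption days enter compliance.

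The cost is a few extra table rows and some SAP wording. The analysis relies on recorded start and stop dates of interruptions. Protocol 11.4.3 presumes these, but Protocol 10.2.5 mentions only the action taken with study drug, so the sponsor should confirm that the dates are captured.
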